### **12.0 Withdrawal of Subjects**

Subjects may withdraw consent to participate in the study at any time. Subjects may be withdrawn from the trial by the study investigators if they fail to return for study visits or follow study instructions, have unacceptable vision or fit with the contact lenses, become pregnant during the trial, or have a study-related adverse event that warrants study withdrawal.

### **13.0 Costs/Payments to Subjects**

There are no expected additional costs to subjects that participate in the study. There is no cost to subjects for contact lens fitting in this study. Subjects will be provided with daily disposable contact lenses for the duration of the study at no charge. Subjects will be provided with a token for parking at each study visit (if necessary). Subjects will be

## **FULL PROTOCOL TITLE:** Toric Contact Lens Performance Study

compensated \$40 for completion of each study visit (a total of up to \$200 for 5 visits). Subjects will be compensated with an Amazon gift cards after completion of the last study visit or exit from the study (if early exit due to withdrawal).

### **14.0 Compensation for Research-Related Injury**

The risks to subjects from participation in the study are minimal. The clinical procedures used in the study are commonly used clinical procedure in optometry and ophthalmology. In the rare case that a subject is injured as part of their participation in the study, the subject will be responsible for any associated medical bills.

### **15.0 Confidentiality**

Subjects will be assigned a unique subject ID. Subjects IDs are two digits and should start at 01 and continue in the order of enrollment. No one outside of the research team will have access to the subject identifiers. A key to the study code will be maintained for 3 years at the time of study completion (i.e. Last Subject, Last Visit).

Any source documents with patient identifiable information will be kept only at the local site (informed consent form, linking log). Individual documents will be kept in a locked room in The Ocular Surface Institute.

### **16.0 Provisions to Protect the Privacy Interests of Subjects.**

Those who are potentially eligible and interested in the study will be referred to a study team member who will discuss the study with the patient. This discussion will take place in a quiet, private area and as much time as necessary will be spent discussing the details of the study.

### **17.0 Informed Consent Process**

This trial will follow the University of Houston Division of Research SOP: Informed Consent Process for Research (HRP-090). The participant will be provided an opportunity to read the informed consent and to have any questions answered before agreeing to participate. Prior to any testing, the investigator or study coordinator will obtain written informed consent from all participants. The consent form will be signed and dated by both the participant and a member of the study personnel who has been approved to obtain consent. The participant will receive a copy of the signed consent documents and the originals will be filed in the subject binder on site in a secure location.

### **18.0 Process to Document Consent in Writing**

## **FULL PROTOCOL TITLE:** Toric Contact Lens Performance Study

The clinical trial will follow the University of Houston Division of Research standard operating procedure regarding written documentation of informed consent (SOP: Written Documentation of Consent (HRP-091)). The consent form will be signed and dated by both the participant and a member of the study personnel who has been approved to obtain consent. The participant will receive a copy of the signed consent documents and the originals will be filed in the subject binder on site in a secure location. A copy of the informed consent document is included in the study related documents.

### **19.0 HIPAA**

We will be collecting demographic information and general medical and eye health information. Since protected health information will be collected, the Health Insurance Portability and Accountability Act (HIPAA) authorization form will be included as part of the Informed Consent process.

The linked PHI will be destroyed upon completion of the study and final analysis/report. PHI will not be reused or disclosed to any other person or entity, except as required by law, for authorized oversight of the research study, or for other research for which the use or disclosure of protected health information for which an authorization or opportunity to agree or object is not required by 45 CFR 164.512.

### **20.0 Data Management**

Paper source documents (i.e. case report forms) will only be associated with a subject ID number and will not contain direct subject identifiers.

### **21.0 Specimen Use and Banking**

No specimens will be collected in this study.

### **22.0 Sharing of Results with Subjects**

Subjects will be unmasked at the end of the study and informed of their contact lens parameters. The subject may choose to share this information with their eye doctor to inform future contact lens fitting needs.

### **23.0 Resources**

The study team completed all necessary ethics training requirements. The co-PIs ([name], OD, PhD and [name], OD, PhD) each have over a decade of experience conducting clinical care and research and will oversee all study personnel.

**FULL PROTOCOL TITLE:** Toric Contact Lens Performance Study

With an abundance of contact lens wearers in the surrounding community, we believe that we should be able to complete enrollment within 6 months.

This study utilizes the clinics of The University Eye Center and The Ocular Surface Institute to recruit study subjects on the campus of the University of Houston.

Title: Toric Contact Lens Performance Study

NCT number: NCT03546647

Document date:

Protocol: 27 Aug 2018

Statistical Analysis Plan:

The treatment effects on pre-specified outcomes that met the parametric assumptions were analyzed using the Grizzle model (Grizzle, 1965) for the two-period two-treatment crossover trial. First, the data were tested for the presence of a carry-over effect according to the sequence of randomization, that is, sphere or toric, during the first period at the critical level of 0.10. Then, the treatment effect was estimated using a linear mixed model in the presence of period and sequence effects to obtain unbiased effect sizes. For pre-specified outcomes that did not conform to non-parametric testing, Koch's approach using the Wilcoxon rank sum test was used. Treatment differences and 95% Confidence Intervals were estimated using the Hodges-Lehmann method. In the presence of any carry-over effects, hypothesis tests were conducted on period 1 only. Unadjusted p-values are reported and inferred using a specified critical region after adjusting for multiple testing. Summary measures of means and standard deviations are reported for variables conforming to parametric testing and median, 25th percentile, and 75th percentile were reported otherwise. A one-sample binomial test was used to test the hypothesis that the probability of subject preference to treatment lens and standard lenses are equally likely. The hypothesis that $H0: \Delta=0$ vs. $HH1: \Delta\neq0$ using a two-sided test with significance level $\alpha=0.05$ was tested, where Δ is the underlying benefit for treatment contact lenses versus spherical contact lenses in this cross-over design. To assess treatment differences in spatial frequency, a repeated measures model was used and tested for the interaction between spatial frequency and lens type. In the presence of a statistically significant interaction, follow-up testing with appropriate Type I error adjustment was used.

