## **4.0 Number of Subjects**

The proposed single-site study will be conducted at The Ocular Surface Institute at the University of Houston College of Optometry. Up to 76 subjects will be screened for study inclusion, with the goal of completing 34 subjects.

Source data will be collected on paper case report forms and then doubly entered electronically into a database by trained personnel. Source data will be quality assured at the levels of coding, scoring, and entry prior to locking the dataset for analysis.

In this within-subject crossover design, a paired t-test will be used to compare primary outcome visual acuity performance of study treatment lens wear to standard spherical contact lens wear among astigmats. We will use a two-sided independent t-test to ensure there are no carry over or period effects in our cross-over design, although it is not anticipated. As a secondary outcome, subjects will be asked their preference of contact lenses in a two-alternative forced choice format. A one-sample binomial test will be used to test the hypothesis that the probability of preference to treatment lens and standard lenses are equally likely ( $H_0: p=.5$  v.  $H_1: p\neq.5$ ).

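### Gating the lens comparison on a carry-over pre-test at 0.10, with a fallback to period 1, turns the stated 0.05 test into one of about 0.07 to 0.09

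*SAP*

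**What the plan says.** The SAP describes a two-stage analysis for the two-period, two-lens crossover. The first stage is a test: "First, the data were tested for the presence of a carry-over effect according to the sequence of randomization", carried out "during the first period at the critical level of 0.10". The second stage is the treatment analysis: "Then, the treatment effect was estimated using a linear mixed model in the presence of period and sequence effects to obtain unbiased effect sizes". Outcomes unsuited to parametric analysis go to a rank-sum approach. The decision rule follows: "In the presence of any carry-over effects, hypothesis tests were conducted on period 1 only". The lens effect is tested two-sided at 0.05. No lower level is given for the period 1 branch.

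On multiplicity the SAP says only: "Unadjusted p-values are reported and inferred using a specified critical region after adjusting for multiple testing". It gives no level and does not link the adjustment to the carry-over gate.

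Protocol section 4.0 plans a paired t-test for the primary acuity outcome and adds: "We will use a two-sided independent t-test to ensure there are no carry over or period effects in our cross-over design". It says carry-over is not expected. It states neither a 0.10 level nor a period 1 fallback, so the gate appears only in the SAP.

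**The concern.** The carry-over test compares subject totals (period 1 plus period 2) between the two sequences. The fallback compares period 1 values between the same two groups. Both contain the period 1 data and are strongly positively correlated. A chance imbalance in period 1 therefore tends both to trigger the fallback and to make the fallback test significant. A period 1 test chosen this way is not a 0.05 test, even though it would be one if planned from the outset. The mixed model's estimate is unbiased if always used, but that does not carry over to a procedure that uses it only when a pre-test is passed.

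Two things are at stake. The stated error rate is not delivered, and the SAP makes no exception for the primary endpoint, binocular near acuity. The within-subject comparison that justifies 34 subjects can also be replaced by a 17 versus 17 parallel-group comparison. Finally, a non-significant test in a trial this small cannot establish that carry-over is absent, which is the purpose protocol section 4.0 gives it.

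**Working it through.** **Inputs.** From the SAP: treatment test two-sided 0.05, pre-test level 0.10. From protocol section 4.0: 34 completers allocated equally (34/2 = 17 per sequence), expected benefit half a line (0.05 logMAR), variability of the within-subject difference 0.1 logMAR. The protocol calls the last figure a variance, but only reading it as a standard deviation reproduces 34. Assumed: ρ, the correlation between a subject's two period measurements, which the documents do not give.

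**The plan's own figure.** A paired t-test with difference/SD = 0.05/0.1 = 0.5 at two-sided 0.05 has power 0.795 with 33 subjects and 0.808 with 34. The stated 34 is reproduced.

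**Type I error of the gated procedure.** Assume no lens effect and no carry-over.

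- The carry-over statistic (sums) is independent of the two-period lens statistic (differences). The branch without fallback therefore contributes 0.90 × 0.05 = 0.045.
- The carry-over statistic has correlation √((1+ρ)/2) with the period 1 statistic. The fallback branch contributes P(|Z period 1| > 1.96 and |Z carry-over| > 1.645), from the bivariate normal. Divided by 0.10, this is the rejection rate given fallback.
- Overall error = 0.045 + 0.10 × (rejection rate given fallback). At ρ = 0.5 the correlation is √0.75 = 0.866, the conditional rate 0.370, and the total 0.045 + 0.037 = 0.082.

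The simulation columns use 17 + 17 subjects: 400,000 trials per ρ for t-tests, 40,000 for rank-sum tests.

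| ρ (assumed) | Correlation of the two statistics | Rejection given fallback | Overall error (normal) | Overall error (simulated t) | Overall error (simulated rank-sum) |
|---|---|---|---|---|---|
| 0 | 0.707 | 0.251 | 0.070 | 0.070 | 0.064 |
| 0.3 | 0.806 | 0.319 | 0.077 | 0.076 | – |
| 0.5 | 0.866 | 0.370 | 0.082 | 0.081 | 0.076 |
| 0.7 | 0.922 | 0.427 | 0.088 | 0.087 | – |
| 0.8 | 0.949 | 0.458 | 0.091 | 0.089 | 0.087 |
| 0.9 | 0.975 | 0.487 | 0.094 | 0.093 | 0.089 |

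As ρ approaches 1 the normal-theory figure tends to 0.045 + 0.10 × 0.50 = 0.095. In the same t-test simulations, always using both periods rejects at 0.049 to 0.050. If the SAP's phrase about the first period is taken literally, as a pre-test on period 1 data alone, the simulated overall error is 0.076 to 0.094.

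**Power at 0.05 logMAR, no carry-over.** The SD of one measurement is 0.1/√(2(1−ρ)): 0.100, 0.129 and 0.158 for ρ = 0.5, 0.7 and 0.8. A 17 versus 17 t-test on period 1, as a stand-alone test, then has power 0.29, 0.19 and 0.15. The two-period test has 0.81 and the gated procedure as a whole 0.78.

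**Power of the pre-test.** The standard error of the between-sequence difference in totals is SD × √(2(1+ρ)) × √(2/17). At ρ = 0.5 this is 0.100 × 1.732 × 0.343 = 0.059. A carry-over of 0.05 logMAR, as large as the lens effect, is then 0.05/0.059 = 0.84 standard errors. Power at the 0.10 level is 21%, 16% and 14% for ρ = 0.5, 0.7 and 0.8. With no carry-over, each outcome still has a 10% chance of triggering the fallback.

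**The case against.** **Multiplicity.** The SAP adjusts its critical region for multiple testing, so an outcome may be tested below 0.05 and its absolute error rate may be under 0.07. That is fair, and the 0.07 to 0.09 must be read as applying to an outcome tested at a full 0.05. The inflation remains in relative terms. At an assumed level of 0.025 the gated rate is 0.037 to 0.047, and at 0.0125 it is 0.020 to 0.023, about 1.5 to 1.9 times the intended level.

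**Wording.** The mixed-model sentence carries no condition, and the period 1 rule follows the non-parametric sentences, so the rule could be read more narrowly. The broader reading is more natural, since the rule refers to hypothesis tests generally. The rank-sum branch is inflated too.

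**Power.** The 15% to 29% figures are unconditional. Because the fallback selects large period 1 differences, power given fallback is about one half, and the procedure loses only about 3 points overall. This stands: the main fault is the error rate, not the power.

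**Protection against real carry-over.** No washout is described, and the second lens is fitted at the visit that measures the first. With a carry-over of 0.05 logMAR and no lens effect, the two-period test rejects about 30% of the time. The gated procedure still rejects 26% to 29% for ρ = 0.5 to 0.8, so the gate offers little protection. The case against carry-over has to come from the design: daily disposable lenses, with outcomes scheduled about a week or more after each fitting.

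**Conclusion.** The concern holds. As written, the SAP's procedure does not deliver its two-sided 0.05. With 17 subjects per sequence and no true effects, the rate is about 0.07 to 0.09 per outcome for ρ between 0 and 0.8, with a ceiling of 0.095. The rank-sum version starts slightly lower, at 0.064. These figures assume approximately normal data (simulated as such for the rank-sum test too), the gate applied to every outcome, and a critical level of 0.05 before any multiplicity adjustment. A lower level scales the absolute rate down but does not remove the inflation. The documents do not show whether the fallback was ever triggered. The error rate belongs to the procedure and is wrong in either case.

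**What to change.** In the SAP, remove the carry-over test as a decision rule and delete the sentence restricting tests to period 1. Make the two-period analysis the sole test for every outcome:

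- **Parametric outcomes:** the linear mixed model with lens and period as fixed effects and subject as random. Keeping the sequence term is acceptable and supplies the sequence contrast.
- **Other outcomes:** the rank-sum test on within-subject period differences, compared between sequences.
- **Carry-over:** report the sequence contrast with its confidence interval, descriptively. Any period 1 result should be labelled a sensitivity analysis.

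In protocol section 4.0, replace the t-test meant to rule out carry-over and period effects with adjustment for period in the model, and give the design reasons for expecting no carry-over.

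The cost is small. No new data are needed, the stated 0.05 is restored, and with no carry-over power rises from 0.78 to 0.81. Because the SAP is written in the past tense, any outcome already judged on period 1 alone should be identified and re-analysed from the data in hand, with the two-period result reported.

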## FULL PROTOCOL TITLE: Toric Contact Lens Performance Study

We aim to test the hypothesis that  $H_0: \Delta=0$  v.  $H_1: \Delta\neq0$  using a two-sided test with significance level  $\alpha=0.05$ , where  $\Delta$  is the underlying benefit for treatment contact lenses versus spherical contact lenses in this cross-over design. Based on previous studies reported average photopic low contrast visual acuity ranged from 0.3 to 0.4 logMAR with various brands of toric contact lenses and under the same conditions from 0.51 to 0.56 with spherical contact lenses among low-to-moderate astigmatic eyes. An estimated improvement with toric lenses has been reported as  $0.07\pm0.14$  among those with low astigmatism with the magnitude of improvement increasing among those with high levels of astigmatism. It is reasonable to expect a detectable range of 2 letters to half-line of improvement with the treatment contact lenses versus the standard sphere lenses. If we expect a half-line treatment benefit and the within-subject variance of the difference in mean visual acuity between the two periods to be a line (0.1 logMar), then based on pilot-study results, and a required 80% power we need 34 participants overall for each study population (68 total). We will randomize an equal number of subjects to each group (i.e., group A receives treatment 1 in period 1 and treatment 2 in period 2; group B receives treatment 2 in period 1 and treatment 1 in period 2). Depending on the variability, a sample size of 34 in each sampled population allows us to detect a smaller effect size (e.g., high contrast tests) as low as 2.5 letters with a within-subject variability of 0.06 logMar. The visual function testing is novel and has not been used on a population of astigmatic contact lens wearers. So sample size planning cannot be done for these tests. We plan to screen up to 38 participants from the study population to allow for attrition.

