## 7.0 Procedures Involved

The study is a clinical trial. Subjects will be randomized to start with either toric lenses or spherical correction. Patients will be seen for 5 visits over a period of approximately 1 month. Visit 1 will determine subject eligibility for the study. Visits 2 and 4 are contact lens follow-up visits. Visits 3 and 5 are study outcome visits. Tests of visual performance at a near reading distance will be evaluated with an iPad application (Optom Central) developed by [name]. This application can measure reading speed, near contract sensitivity and can provide information on how a subject interacts with the electronic device (e.g. blink rate, working distance from the device, scrolling and zooming on the page, etc.). This application is designed for research purposes only and is not commercially available in the Apple App Store.

Visit 1: Screening, Enrollment and Baseline		
Step	Item	Details
1.1.1	Informed Consent	Review and complete the informed consent form
1.1.2	Subject Demographics	Collect subject demographic data
1.1.3	Medical/Ocular History	Collect subject history including contact lens history
1.1.4	Concomitant Medications	Collect information on concomitant medications
1.1.5	Distance and Near Visual Acuity	Perform Distance and Near Snellen and LogMAR acuity OD/OS with the patient's habitual correction.
1.1.6	Questionnaires	Administer the NAVQ to the subject

**FULL PROTOCOL TITLE:** Toric Contact Lens Performance Study

1.1.7	Contrast Sensitivity	Perform the contrast sensitivity test on the iPad
1.1.8	Radner reading test	Perform the Radner reading speed test on the iPad
1.1.9	Functional Vision testing with iPad	Perform the functional vision test on the iPad
1.1.10	Auto-Refraction / Auto-keratometry	Perform autorefraction/keratometry with open field machine
1.1.11	Refraction	Perform Manifest Refraction using maximum plus to best visual acuity
1.1.12	Accommodation, binocular vision	Conduct negative relative accommodation and positive relative accommodation test, Modified Thorington Test at distance and near
1.1.13	Pupil size	Measure pupil size OD/OS in dim and bright light settings
1.1.14	Slit Lamp Exam with NaFl staining	Instill 1 drop of NaFL and evaluate slit lamp findings using the CCLRU grading scale
1.1.15	Check of eligibility and lens order randomization	Confirm eligibility criteria are met. If so, use randomization table to determine order of lens wear

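### After a carry-over flag the SAP moves the hypothesis test to period 1 but does not say that the estimate and interval move too, and the period-1 test uses none of the Visit 1 baselines

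*SAP*

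**What the plan says.** The SAP tests carry-over by randomised sequence "during the first period at the critical level of 0.10". For outcomes analysed parametrically it continues: "Then, the treatment effect was estimated using a linear mixed model in the presence of period and sequence effects to obtain unbiased effect sizes". Outcomes analysed by ranks get a Hodges-Lehmann difference with a 95% interval. Neither estimation rule depends on the carry-over result. The only consequence of a flag is: "In the presence of any carry-over effects, hypothesis tests were conducted on period 1 only". No baseline covariate is named for any analysis.

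The protocol (4.0 Number of Subjects) plans an independent t-test for carry-over and period effects, with no threshold and no fallback.

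The Visit 1 table (7.0 Procedures Involved) lists the NAVQ, contrast sensitivity, Radner reading and functional vision before randomisation. The same four tests recur at Visits 3 and 5. For acuity, Visit 1 has "Perform Distance and Near Snellen and LogMAR acuity OD/OS", and that row specifies habitual correction. The primary endpoint (6.0 Study Endpoints) is binocular near acuity, measured OU in the study lens at Visits 3 and 5. Low-contrast acuity is not listed at Visit 1.

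**The concern.** Three things follow from the fallback sentence.

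- **The source of the estimate is not stated after a flag.** On the literal reading, estimate and p-value come from different data. A reader could see a two-period interval that excludes zero beside a non-significant period-1 test, or the reverse.
- **The description as unbiased has no condition.** It fails in the case the flag is meant to detect, because a sequence term does not remove differential carry-over from the lens contrast.
- **The period-1 comparison is the weakest analysis in the plan.** It is a parallel comparison of half the sample with the other half. As written it is unadjusted, although relevant pre-randomisation values are already collected.

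The first two affect what is reported for any flagged outcome. The third is a loss of precision, separate from the mismatch.

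**Working it through.** **Inputs from the documents.** Protocol 4.0 gives two-sided alpha 0.05, 80% power, a half-line benefit (0.05 logMAR), a variability of the between-period difference of 0.1 logMAR, 34 completers and equal allocation, so 17 per sequence. The SAP gives 0.10 for the carry-over test. The protocol calls the 0.1 a variance, but its sample size reproduces only if 0.1 is read as an SD.

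**Plan's own figure.** Paired t-test, noncentrality (0.05/0.1) × √34 = 2.92, 33 df: power 0.808. The smallest n reaching 0.80 is 34, so the stated 34 is reproduced.

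**Assumption.** The documents give no between-period correlation ρ. I use 0.5 to 0.9. Single-period SD = 0.1/√(2(1−ρ)) = 0.100, 0.129 and 0.224 at ρ = 0.5, 0.7 and 0.9.

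**Bias of the two-period estimate.** Sign benefit as positive, with true benefit δ and differential carry-over c of the toric lens into the following sphere period. Period means, apart from common terms, are δ then c (toric first) and 0 then δ (sphere first). The lens contrast is [(δ − c) − (0 − δ)]/2 = δ − c/2. A sequence effect cancels within subject, so including it changes nothing here. With δ = c = 0.05 the expectation is 0.025; simulation gave 0.025.

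**Why the two analyses diverge.** The carry-over test uses subject totals. Its correlation with the period-1 value is √((1+ρ)/2): 0.87 at ρ = 0.5 and 0.97 at ρ = 0.9. With equal variances, its correlation with the within-subject difference is zero. A flag therefore selects extreme period-1 contrasts and leaves the two-period contrast alone.

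**Disagreement on significance at 0.05 among flagged trials** (60,000 simulated trials per row and ρ; two-period t-test v period-1 t-test):

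| True benefit | Carry-over | ρ = 0.5 | ρ = 0.7 | ρ = 0.9 |
|---|---|---|---|---|
| 0 | 0 | 37% | 42% | 48% |
| 0 | 0.05 | 41% | 44% | 48% |
| 0.05 | 0 | 50% | 50% | 48% |
| 0.05 | 0.05 | 54% | 54% | 51% |

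Repeat runs with other random seeds, adding carry-over 0.03 with the half-line benefit, stay within about 36% to 56%. This is the range over these scenarios, not a bound. With no true carry-over about 10% of trials are flagged per outcome, so the unconditional rate is about 0.10 × 0.37 to 0.10 × 0.50, or 4% to 5%.

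**Period-1 power for a half-line, 17 v 17.** At ρ = 0.5, SE = 0.100 × √(2/17) = 0.0343, noncentrality 0.05/0.0343 = 1.46, power 0.29. At ρ = 0.7 and 0.9 it is 0.20 and 0.10.

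**With a baseline covariate** (assumed correlation 0.5 with the outcome, ρ = 0.5): residual SD 0.100 × √(1 − 0.25) = 0.0866, SE 0.0297, noncentrality 1.68. The formula gives power 0.37; fitting the model in simulation gives about 0.36. Among flagged trials with no lens effect and no carry-over, false positives fall from about 36% to 22%, and root mean squared error from 0.063 to 0.048 logMAR.

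**Quality of the period-1 estimate after a flag.** With δ = 0.05, carry-over of 0.03 or 0.05 and ρ = 0.5, it averages about 0.085 unadjusted and about 0.075 adjusted. Over ρ = 0.5 to 0.9 the unadjusted root mean squared error is 0.048 to 0.155, against 0.017 to 0.031 for the two-period estimate.

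**The case against.** The strongest reply is that the SAP nowhere says the estimate stays on two periods. The estimation sentence comes before the fallback and can be read as the default that the fallback overrides. That stands: a reader might infer a stated rule to report a two-period estimate after a flag, but the documents only fail to say that the estimate moves. The SAP also names 95% intervals only with Hodges-Lehmann, so the two-period t interval compared here is itself an assumption.

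Second, moving the estimate to period 1 makes it consistent with the test but not better. Its error after a flag was larger than that of the two-period estimate throughout the simulations. This also stands, and is why the fix shows both estimates with a warning.

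Third, a reader might infer that ignoring the baseline causes the contradiction, or that Visit 1 supplies a matching baseline for the primary endpoint. Neither is supported. The contradiction comes from using different data; omitting a covariate only costs precision. Visit 1 near acuity is monocular in habitual correction, so it is a proxy for a binocular study-lens outcome.

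Finally, the branch may rarely matter. The protocol does not anticipate carry-over, the lenses are daily disposable, the second outcome visit is about 10 days after the switch, and a carry-over of 0.05 equals the whole assumed benefit. But chance alone flags about 10% per outcome, and the plan has several outcomes.

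**Conclusion.** The point holds as a gap in reporting rules with a cheap gain in precision. After a flag, the SAP does not say which data supply the estimate and interval. Its claim of unbiasedness is wrong as written if differential carry-over is present, by half its size. On the literal reading, about 36% to 56% of flagged trials in the scenarios examined give conflicting significance. These figures rest on 17 per sequence, 0.1 logMAR read as an SD, and an assumed ρ of 0.5 to 0.9.

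The baseline part applies directly to the NAVQ, contrast sensitivity, Radner reading and functional vision, by proxy to high-contrast near acuity, and not to low-contrast acuity. The gain from 29% to 36% power depends on two assumed correlations of 0.5 and still leaves period 1 far below the 81% of the crossover analysis.

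The larger defect of the same sentence is untouched. With no true carry-over the unadjusted two-stage rule has an overall type I error of 0.082 to 0.093 against a nominal 0.05. Even with the covariate, 22% false positives among flagged trials is more than four times nominal.

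**What to change.** If the period-1 branch is kept:

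1. Fit the period-1 model with the Visit 1 value as covariate for the NAVQ, contrast sensitivity, Radner reading and functional vision. For high-contrast near acuity use the mean of OD and OS near logMAR, stated to be a proxy (monocular, habitual correction). Note that low-contrast acuity has no listed baseline.
2. Take p-value, estimate and interval from that one model. Show the two-period estimate beside it and label both. Warn that a period-1 estimate selected by a flag is imprecise and, if carry-over is real, biased, and that the two-period estimate is off by half the differential carry-over.
3. Make the description of the mixed-model effect sizes as unbiased conditional on there being no differential carry-over.
4. Because the SAP is written in the past tense, list which outcomes were flagged and which data gave each estimate and p-value.

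The cost is a few sentences, one degree of freedom per model and no new data. Items 1 and 2 fall away if the pre-test branch is removed and the two-period analysis is reported throughout; the condition in item 3 should then still be stated.
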